3. STUDY DESIGN

This is an open label, block randomised (10 in each block), mixed method (quantitative and qualitative) study to be conducted for a period of up to 16 weeks

Children aged between 6-16 years with asthma attending the paediatric respiratory difficult asthma clinic will be recruited into the study and randomly allocated to one of three arms using block randomisation matched for age and size of group. Children will be assigned to trial one of the following four NEMD's to be tested:

1. Block 1 (10): Smartinhaler Plus™ (Adherium, New Zealand)
 - This measures inhalation usually flow sensors and is the next generation of a currently commercially available EMD
2. Block 2a (5) : Flo-Tone (Clement Clarke, UK) plus Rafi-tone, acoustic enabled Smartphone App (clin-e-cal, UK) for children aged 6 – 11 years
 - The Flo-Tone attaches to an MDI and makes a sound when the inhaler is used correctly. Rafi-tone is a Smartphone App that detects the sound and activates a game. The game is aimed at younger children and therefore children aged 6 – 11 years will be randomised to this block.
- Block 2b (5) : Inhaler Compliance Assessment (INCA™) device (INCA, Ireland)
 - This is an audio recording device which attaches to a Diskus dry powder inhaler. Analysis of the digital audio recordings enables objective assessment of inhaler use and technique. As it can only be used with a Diskus only children ≥ 12 years will be randomised to this block
3. Block 3: Video and Remote Directly Observed treatment (rDOT)
 - Children are filmed on a Smartphone using their inhaler. The clip is then automatically uploaded via a Smartphone App (Continga, UK) and reviewed by a Clinical Nurse Specialist to ensure inhaler technique is correct.

Recruitment

30 children will be recruited into the study; 10 per block (5 per block aged 6-11 years and 5 aged 12-16 years)

Visit 1: Novel electronic monitoring device (NEMD) issued

Routine clinical care assessments will be carried out at the end of the study period as below, including asthma control test (ACT) or the childhood asthma control test (cACT), exhaled nitric oxide (FeNO) and spirometry (FEV1 and BDR) .

Patient/parent/Carer will be invited to take part in the study.

Information regarding the study and its objectives will be communicated to the Patient/parent/carer in both oral and written form using patient information leaflets.

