The focus group interviews will be used to assess the usability and acceptability of the devices

➤ Quantitative data

The amount of usable data from each device will be quantified and compared.

This will provide data on the perceived accuracy of the device.

Additionally, data on asthma control and quality of life will be assessed.

These will be analysed quantitatively statically using the Statistical Package for the Social Services (SPSS). Data will be tested for normality using visual inspection, histograms and Kolmogorov-Smirnov testing. Parametric tests will be used if the data is normally distributed. If the data is not normally distributed or there are only small numbers non parametric tests will be used or the data will be logarithmically transformed. The significance levels for all tests will be set at <0.5.

Comparative analysis of variance between 2 groups for continuous data will be performed using the student's t test for normally distributed data and the Mann Whitney U tests for non normally distributed data and for more than 2 groups the ANOVA or Kruskal Wallis respectively. A comparison of the proportions between groups will be performed using the Pearson Chi 2 tests.

The quantitative and qualitative results will be amalgamated and an evidence report prepared to assess the feasibility of each device.

An expert panel will be convened to select the most appropriate device to take forward to a larger randomised controlled trial to assess the impact of the device on adherence in children with asthma.

Data and all appropriate documentation will be stored for a minimum of 10 years after the completion of the study, including the follow-up period.

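### Pearson chi-square is the only test named for proportions, yet two devices have 5 children each, so p-values in comparisons with those arms can be too small (minor)

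*Combined protocol and SAP*

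**What the plan says.** The quantitative part of section 7 gives a single rule for proportions: "A comparison of the proportions between groups will be performed using the Pearson Chi 2 tests". The same section says that the quantity of usable data will be compared across devices, so the unit of comparison is the device.

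Section 7 does foresee small samples: "If the data is not normally distributed or there are only small numbers non parametric tests will be used or the data will be logarithmically" (the sentence closes there with the log transformation). It belongs to the choice between parametric and non-parametric methods.

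Section 3 sets the group sizes: "30 children will be recruited into the study; 10 per block (5 per block aged 6-11 years and 5 aged 12-16 years"). Block 1 is one device with 10 children. Block 2 is split by age between two devices: "Block 2a (5) : Flo-Tone (Clement Clarke, UK") with its companion app for ages 6 to 11, and "Block 2b (5) : Inhaler Compliance Assessment (INCA™) device (INCA, Ireland") for ages 12 and over. Block 3 (remote directly observed treatment) has 10 children by the per-block figure. The four device groups are therefore 10, 5, 5 and 10.

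**The concern.** The Pearson test refers its statistic to a chi-square distribution, an approximation that is conventionally trusted when every expected count is about 5 or more. With 5 children in an arm that condition cannot be met for a binary outcome, whatever the data turn out to be. This is known at the design stage.

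The small-numbers sentence does not help. Pearson chi-square is already non-parametric, and a log transformation does not apply to a yes/no outcome. So the plan has a fallback for continuous measures and none for proportions.

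At stake is the accuracy of any p-value for a proportion that enters the evidence report. If no rule is fixed beforehand, the choice between Pearson and an exact test would also be made after the data are seen.

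**Working it through.** **Inputs.** Device groups of 10, 5, 5 and 10 (section 3). Test: uncorrected Pearson chi-square (section 7). Level: 0.05, which is an assumption. Section 7 prints "The significance levels for all tests will be set at <0.5", and that is a separate issue.

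**The plan's own computable figure.** Section 7 cites 29 participants for seeing a theme of 10% prevalence at least twice with 80% probability. 1 − 0.9^29 − 29 × 0.1 × 0.9^28 = 0.801, against 0.785 at n = 28, so 29 reproduces. It has no bearing on the test for proportions.

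**Step 1: expected counts.** With s successes among N children, the smaller expected count in the smaller arm of size n is n × min(s, N − s)/N. Its largest possible values are:
- 5 v 5: 5 × 5/10 = 2.5
- 10 v 5: 5 × 7/15 = 2.33
- 10/5/5/10: 5 × 15/30 = 2.5
- 10 v 10: 10 × 10/20 = 5

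Only the smallest count is bounded in this way. The other cell of a 5-child arm is at least 2.5. Any loss of children from a 5-child arm lowers the bound.

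**Step 2: one 5 v 5 table, 5/5 v 2/5.** Expected successes are 3.5 per arm and expected failures 1.5.
- Pearson: 2 × 1.5²/3.5 + 2 × 1.5²/1.5 = 1.286 + 3.000 = 4.286, p = 0.038.
- Fisher: 2 × C(5,5) × C(5,2)/C(10,7) = 2 × 10/120 = 0.167.
- Unconditional exact (tables ordered by the Pearson statistic, probability maximised over the common proportion p, q = 1 − p): ten tables are at least this extreme, with total probability 2 × (10p³q⁷ + 10p⁷q³ + 5p⁴q⁶ + 5p⁶q⁴ + p⁵q⁵). At p = 0.5 this is 62/1024 = 0.061. The maximum is 0.062, near p = 0.38.

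These ten tables are exactly those with Pearson p < 0.05, so 0.062 is also Pearson's maximum true error for 5 v 5.

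**Step 3: one 10 v 5 table, 0/10 v 2/5.** Expected successes are 1.33 and 0.67; expected failures are 8.67 and 4.33.
- Pearson: 1.333² × (1/0.667 + 1/1.333 + 1/4.333 + 1/8.667) = 4.615, p = 0.032.
- Unconditional exact: 0.042.
- Fisher: C(5,2)/C(15,2) = 10/105 = 0.095.

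Similarly, 2/10 v 4/5 gives 0.025, 0.041 and 0.089.

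**Step 4: all tables, at 0.05.**

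| Comparison | Max. true error, Pearson | Max. true error, Fisher | Pearson-significant tables | of which not by Fisher | of which not by unconditional exact |
|---|---|---|---|---|---|
| 5 v 5 | 6.2% | 2.1% | 10 | 4 | 4 |
| 10 v 5 | 5.0% | 2.8% | 22 | 6 | 0 |
| 10 v 10 | 4.2% | 1.3% | 46 | 12 | 0 |

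For the four-device table the maximum true error of Pearson is 4.8%, over common proportions from 0.05 to 0.50. Swapping success and failure gives the same for 0.50 to 0.95.

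The zero for 10 v 5 is narrow. The least extreme significant tables (for example 1/10 v 3/5, Pearson 0.039) have an unconditional p equal to the maximum true error, which is only just under 0.05.

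**The case against.** **Error control is mostly sound.** A reader might infer from expected counts below 2.5 that Pearson's false-positive rate is generally inflated. The enumeration does not support that: at 0.05 the excess is about one percentage point for 5 v 5 and absent elsewhere. This part of the objection stands in full.

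**Disagreement with Fisher overstates the problem.** One could cite 4 of 10, 6 of 22 and 12 of 46 tables as false claims of significance. Fisher is itself conservative at these sizes (2.1%, 2.8% and 1.3%). Against the unconditional test the counts are 4, 0 and 0. The p-values for 10 v 5 remain somewhat low, but no conclusion at 0.05 changes.

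**The one comparison where conclusions change is hard to interpret anyway.** The only 5 v 5 device comparison sets ages 6 to 11 against ages 12 and over, so device and age cannot be separated by any test.

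**Little may rest on it.** The documents name no binary endpoint or responder threshold, and most of the listed quantitative measures are continuous. A reader might infer that a single p-value could decide which device goes forward. Sections 3 and 7 say instead that quantitative and qualitative results are combined and an expert panel selects. The primary outcome is acceptability and usability, assessed by thematic analysis.

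**The bound depends on comparing devices.** If Block 2 were pooled and three blocks of 10 compared, the smallest expected count could reach 5. Section 7 refers to each device, so the device-level reading is the natural one.

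These points limit the size of the concern. They do not remove it: the plan commits to testing proportions with a method whose p-values can be too small at its own 5-child group sizes.

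**Conclusion.** The point holds as a minor one. In comparisons that include a 5-child device, the smallest expected count is at most 2.5 and Pearson p-values can be too small. For 5 v 5 this can move a result across an assumed 0.05 (0.038 against 0.062 unconditional, 0.167 Fisher), with a maximum true error of 6.2%. For 10 v 5 it shifts individual p-values (0.032 against 0.042) without changing a conclusion.

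The documents do not support a claim of general error inflation, nor one that device selection turns on such a p-value. The figures assume a level of 0.05, full recruitment to 10/5/5/10, a binary outcome and Pearson without continuity correction. At the printed 0.5 the table counts do not apply, and that threshold needs correcting on its own account.

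**What to change.** Add to section 7: for any comparison of proportions that includes a device with 5 children, an exact test replaces Pearson chi-square. For two devices use an unconditional exact test, with tables ordered by the Pearson statistic. Use Fisher's exact test if the software does not offer that, and Fisher-Freeman-Halton for more than two devices. Fix the choice before the data are seen.

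Report each device's proportion with an exact confidence interval. The interval shows how little 5 children can establish: for 5/5 the exact 95% lower limit is 0.025^(1/5) = 0.48.

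The cost is one sentence and some sensitivity. For 5 v 5, either two-device exact test drops the same four of ten tables, which brings the maximum true error from 6.2% to 2.1%. For 10 v 5 the unconditional test drops none and Fisher drops 6 of 22, so the unconditional test is preferable where it is available.

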8. REGULATORY ISSUES

8.1 ETHICS APPROVAL

The Study Coordination Centre has obtained approval from the **xxx** Research Ethics Committee (REC) and Health Regulator Authority (HRA). The study must also receive confirmation of capacity and capability from each participating NHS Trust before accepting participants into the study or any research activity is carried out. The study will be conducted in accordance with the recommendations for physicians involved in research on human subjects adopted by the 18th World Medical Assembly, Helsinki 1964 and later revisions.

8.2 CONSENT

Consent to enter the study will be sought from each participant only after a full explanation has been given, an information leaflet offered and time allowed for consideration. Signed participant consent will be obtained. The right of the participant to refuse to participate without

giving reasons must be respected. After the participant has entered the study the clinician will remain free to give alternative treatment to that specified in the protocol at any stage if he/she feels it is in the participant's best interest, but the reasons for doing so will be recorded. In these cases the participants will remain within the study for the purposes of follow-up and data analysis. All participants are free to withdraw at any time from the protocol treatment without giving reasons and without prejudicing further treatment.

8.3 CONFIDENTIALITY

The Chief Investigator will preserve the confidentiality of participants taking part in the study and is registered under the Data Protection Act.

8.4 INDEMNITY

Imperial College London holds negligent harm and non-negligent harm insurance policies which apply to this study.,

8.5 SPONSOR

Imperial College London will act as the main Sponsor for this study. Delegated responsibilities will be assigned to the NHS trusts taking part in this study.

8.6 FUNDING

Asthma UK are funding this study.

Participants will receive reimbursements costs for travel and for refreshments when attending the focus group meeting.

8.7 AUDITS

The study may be subject to inspection and audit by Imperial College London under their remit as sponsor and other regulatory bodies to ensure adherence to GCP and the NHS Research Governance Framework for Health and Social Care (2nd edition).

9. STUDY MANAGEMENT

The day-to-day management of the study will be co-ordinated through [name].

10. PUBLICATION POLICY

The study results will be submitted in abstract to National and international conferences and submitted for publication in appropriate peer reviewed journals.

Appendix 1. Summary of investigations, treatment and assessments

Study Procedures	Screening	During treatment: Visits		Follow up (7 days)	Follow up (4 weeks)	Follow up (up to 16 weeks)	Follow up (up to 6months)
		1	2				
Informed consent	√						
Inclusion/exclusion criteria	√						
Medical history		√	√				
Demographics	√						
Rotuine clinical care monitoring: Spirometry FeNO Asthma control test			√	√			
Quality of Life Questionaires		√	√				
Prescription uptake		√	√				
Adherence monitoring				√	√	√	
End of visit							√
Telephone call				√	√		
Provision of novel electronic monitoring device		√					
Data download				√	√	√	
Focus group or one to one interviews							√
